8. MILESTONES

The anticipated schedule is as follows:

March 2006 Open trial to recruitment

March 2010 400 patients recruited; close trial to recruitment

March 2012 Final analysis

9. SAFETY REPORTING

Definition of an Adverse Event (AE)

An Adverse Event (AE) is any unfavourable and unintended sign (including an abnormal laboratory finding), symptom or disease temporarily associated with the use of a medical treatment or procedure regardless of whether it is considered related to the medical treatment or procedure (attribution of unrelated, unlikely, possible, probable, or definite).

Definition of a Serious Adverse Event (SAE)

An SAE is defined as any untoward and unexpected occurrence that:

- a) Results in death
- b) Is life-threatening* (at the time of the event);
- c) Requires inpatient hospitalisation or prolongation of existing hospitalisation**;
- d) Results in persistent or significant disability or incapacity;
- e) Consists of a congenital anomaly or birth defect;

*The term 'life threatening' in the definition of 'serious' refers to an event in which the patient was at risk of death at the time of the event; it does not refer to an event that hypothetically might have caused death if it were more severe.

**Hospitalisation is defined as an in-patient admission, regardless of length of stay, even if the hospitalisation is a precautionary measure, for continued observation. Hospitalisation for pre-existing condition, including elective procedures, which has not worsened, does not constitute a serious adverse event.

NCI Common Toxicity Criteria for Adverse Events

This study will collect adverse events using the Common Toxicity Criteria for Adverse Events (CTCAE) version 3.0. An electronic version may be accessed through the web at http://ctep.cancer.gov/. The CTCAE (Version 3.0) provides a descriptive terminology that is to be used for adverse event reporting. A grading (severity) scale is also provided in the CTCAE for each adverse event term.

[figure not shown]
Expected and Unexpected Events

The following events associated with radiation treatment are anticipated. Refer to the NCI CTCAE for grading criteria of AEs.

The following table provides the expected adverse events:

Adverse Events					
Incidence between 50%-95%	Incidence between 10%-20%	Incidence 5% or less			
skeletal muscle fibrosis	moist desquamation	anorexia			
erythema	lymphoedema	insufficiency fracture			
epilation	dry skin	osteoporosis			
pigmentation/depigmentation	nausea	radiation induced malignancy			
induration	aesthenia	peripheral nerve fibrosis			
Joint stiffness/immobility		brachial/sciatic nerve plexopathy			
dry desquamation		diarrhoea			
lethargy		tenesmus			
		haematuria			
		bone necrosis			
		bone deformity			
		anaemia			
		reduced bone marrow reserve			
		Bowel			
		ulceration/perforation/steno sis			
		Rectal bleeding			
		frequency/dysuria/cystitis			

An unexpected adverse event is any event that is not listed as an expected adverse event in the section above.

Grading of Adverse Events

The severity of each event should be graded using the CTCAE criteria, if applicable. If the

event is not in the CTCAE, the following categories should be used when determining the

severity of an adverse event.

0 No adverse event or within normal limits

1 Mild adverse event

2 Moderate adverse event

3 Severe adverse event

4 Life threatening or disabling adverse event

5 Fatal adverse event

Causality of Adverse Events

Attribution should be determined and reported. The following categories should be used

when determining whether an adverse event is related to medical treatment or procedure:

Definite Clearly related to investigational agent/ procedure

Probable Likely related to investigational agent/ procedure

Possible May be related to investigational agent/ procedure

Unlikely Doubtfully related to investigational agent/ procedure

Unrelated Clearly NOT related to investigational agent/ procedure

Reporting Serious Adverse Events

On becoming aware that a patient has experienced an SAE, the Investigator must

immediately (within 24 hours):

Complete a SAE Form

• Send by fax the signed and dated SAE Form to the VORTEX Study Office along with

the fax cover sheet provided in the Site Folder:

[contact]

A receipt of the SAE form will be faxed back to the centre within 2 working days. Please Telephone the **VORTEX Study Office** to inform the Trial Co-ordinator if a fax is not received.

2: [name]

 NOTIFY the NHS Trust as determined by local policy (there is no requirement to report SAE's to LREC unless this is part of local policy).

Documenting Serious Adverse Events

Is the responsibility of the local Investigator to assess causality, seriousness and expectedness when reporting an SAE. The Chief Investigator (or Deputy) will also independently determine the causality, seriousness and expectedness of the event. Is the responsibility of the Chief Investigator or designee to report SAEs to the main REC and DMC.

The VORTEX Study Office will send a safety report to MREC annually and copy all investigational sites.

Data Monitoring Committee

The data will be supplied to an independent DMC, which will be asked to give advice on whether the accumulated data from the trial, together with the results from other relevant trials, justifies the continuing recruitment of further patients. The committee will meet one year after the trial opens and then annually thereafter until the trial closes to recruitment. The DMC may consider discontinuing the trial if the recruitment rate or data quality are unacceptable or if the trial compromises patient safety in any way. The trial would also stop early if the interim analyses showed differences between treatments in terms of local relapse that were deemed to be unacceptable to the clinical community or showed differences in limb functioning that was deemed to be convincing to the clinical community.

Follow-up of Serious Adverse Events

In the case of an SAE, the subject must be followed-up until clinical recovery is complete or until disease has stabilised. Follow-up may continue after completion of protocol treatment if necessary. Follow-up information will be noted on the SAE Form by ticking the box marked 'follow-up' and sending to the VORTEX Study Office as information becomes available. Extra annotated information and/or copies of test results should also be provided where available.

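### The SAE definition admits only unexpected events, so read literally a serious event on the protocol's expected list triggers no SAE reporting

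*Protocol*

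**What the plan says.** All the relevant text is in Protocol section 9.

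- **SAE definition.** "An SAE is defined as any untoward and unexpected occurrence that" meets one of criteria a to e: death, threat to life, admission or prolonged admission, lasting or significant disability, or congenital anomaly.
- **Expected and Unexpected Events.** The table is introduced with "The following table provides the expected adverse events", and the text after it says "An unexpected adverse event is any event that is not listed as an expected adverse event in the section above". Neither sentence limits expectedness by grade, severity or outcome.
- **The table.** The column for an incidence of 5% or less has 16 entries. They include "radiation induced malignancy", "brachial/sciatic nerve plexopathy", bowel ulceration, perforation or stenosis, insufficiency fracture and "bone necrosis".
- **Reporting and documenting.** An SAE triggers the SAE form and a fax to the study office within 24 hours. It is the "responsibility of the local Investigator to assess causality, seriousness and expectedness when reporting an SAE". The Chief Investigator or deputy then makes the same three judgements independently, and the Chief Investigator or designee reports SAEs to the main ethics committee and the DMC.
- **Follow-up.** Patients with an SAE are followed until recovery or stabilisation.

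**The concern.** Seriousness and expectedness are separate properties of an event. Seriousness normally decides whether a site must report at once; expectedness is then judged on what was reported. Here the two are merged in the entry condition, and unexpectedness is fixed by a list. The list contains events that can plainly meet criteria a to d.

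A site that follows the definition exactly would send no SAE report for an admission with bowel perforation or for a disabling plexopathy. A site that notices the instruction to rate expectedness may conclude that expected events also qualify, and report the same case. SAE counts would then depend partly on how each site read the section. The DMC, which may consider stopping the trial on patient-safety grounds, would receive an uneven record of the serious events that radiotherapy is known to cause.

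**Working it through.** No sample size, power or error rate is involved, so the check is mainly textual.

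**Step 1. Combine the two definitions.** From the SAE definition, SAE = serious (a to e) AND unexpected. From the expectedness text, unexpected = not in the table. Hence SAE = serious AND not in the table.

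| Event | In the table? | SAE as written? | Possible expectedness rating |
|---|---|---|---|
| Serious | No | Yes | Unexpected only |
| Serious | Yes | No | None; no SAE report exists |
| Not serious | Either | No | None |

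**Step 2. What the second row loses.** The SAE form, the 24-hour fax, the onward report to the ethics committee and DMC, and SAE follow-up are each stated for SAEs. No other part of the protocol extends them to serious events on the list.

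**Step 3. Test against the expectedness rating.** In the first row, the only row with an SAE, expectedness can take one value. The rating by the site and the second rating by the Chief Investigator therefore carry no information. They would carry information only if listed events could be SAEs.

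**Step 4. Other routes for listed events.**
- Soft tissue and bone toxicity on the RTOG scale is a secondary outcome (section 2). Late morbidity is assessed at each visit from 6 months (sections 3 and 5), and all primary and secondary outcomes go to the DMC at the annual interim analyses (section 6).
- Appendix 3 grades skin, subcutaneous tissue, bone and joint. Bone necrosis and spontaneous fracture are grade 4 there, so those events have a scheduled route to the DMC, though not a 24-hour one.
- Bowel, nerve plexus and second malignancy are not on that scale. Section 5 nevertheless names the brachial plexus and small intestine among the organs of concern near the fields.
- Section 9 says that adverse events are collected with CTCAE version 3.0. The form list in section 10 names no general adverse event form. It also omits the SAE form, so it is not exhaustive and its silence proves little.

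**Step 5. Scale.** With 400 planned patients (section 3), one event at the 5% ceiling of its column would affect at most 0.05 × 400 = 20 patients at any severity. If a share s of these were serious, the number would be at most 20 × s. The protocol gives no s, so the serious cases could be anywhere from 0 to 20 for such an event.

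**The case against.** **The rating may be a check on the definition.** Investigators are asked to rate seriousness as well as expectedness, and seriousness is equally fixed by the definition. The step can be read as confirming that the event belongs in the system. This is a fair reading. A reader might call the two parts of section 9 a flat contradiction, but the documents support only redundancy. The redundancy hints at the intent, and the literal exclusion of serious listed events remains on either reading.

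**The harms are seen elsewhere.** Bone and soft-tissue toxicity reaches the DMC every year through the RTOG scores, deaths are captured through overall survival, and adverse events are said to be collected under CTCAE. This stands and it narrows the point. A reader might infer that serious listed events go unrecorded altogether; the protocol does not support that. What is lost is prompt SAE reporting and follow-up, and it matters most where the RTOG scale does not reach.

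**The exemption may be deliberate.** A trial may choose not to expedite well-known toxicities. But where section 9 intends an exemption it states one, as it does for admissions for pre-existing conditions that have not worsened. It gives no such statement for listed toxicities, and no substitute route for the serious ones.

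**Conclusion.** The point holds as a defect in the wording of SAE reporting. Followed exactly, section 9 excludes every listed event from SAE reporting, whatever its outcome. The practical gap is widest for bowel, plexopathy and second-malignancy events, because these fall outside the RTOG scale. Sites may also differ in what they send. No outcome definition, analysis or sample size is affected.

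Two stronger inferences should be resisted. One is a count of missed serious cases, for example 4 to 20 from an assumed incidence of 1% to 5% in 400 patients. That treats every occurrence as serious, and the table gives neither a serious share nor a lower limit for the column. The other is that these are the harms on which the arms are most likely to differ. The background in section 1 links field size to fibrosis, joint stiffness and, marginally, oedema. It says nothing of the kind about perforation, plexopathy or second cancers.

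The conclusion assumes that sites apply the definition as written and that no separate site instruction, not shown here, overrides it.

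**What to change.** Remove the unexpectedness condition from the SAE definition, so that meeting one of criteria a to e is enough to trigger the form and the 24-hour report. Keep expectedness as an attribute rated by the local investigator and the Chief Investigator, as section 9 already asks. That rating then does real work.

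If exempting listed events was intended, reconcile the section the other way: say expressly that listed events are exempt, and state how serious ones reach the study office and the DMC, in particular those outside Appendix 3.

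The first option deletes two words. Its cost is some additional SAE forms for sites and the study office; the protocol gives no basis for estimating how many.

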6. STATISTICAL CONSIDERATIONS

Analysis of outcome measures

The primary research hypothesis for the trial is that a reduced volume of post-operative radiotherapy treatment for adult extremity soft tissue sarcomas will improve limb function without compromising local control. Secondary research hypotheses are that the reduced treatment improves toxicity, overall level of disability and is not inferior to the standard treatment in terms of disease-free survival and overall survival.

The primary analysis for the trial is to compare the experimental treatment to the control treatment in terms of benefit to limb function and non-inferiority for time to local recurrence. For limb function, TESS will be analysed using longitudinal statistical methods, in particular summary measures analysis. The two treatment groups will be compared in terms of TESS at 2 years and area under the curve using either t-tests or Wilcoxon tests depending on the distribution of the data. The proportion of patients in each treatment arm who report small, medium or large change (with worsening or improvement reported separately) between each assessment interval will be required. For time to local relapse, statistical analysis will be based on a one-sided 95% confidence interval for the hazard ratio and non-inferiority will be inferred when the entire confidence interval falls above the non-inferiority margin of 0.63 (equivalent to a difference of 80% versus 70% in 2-year local relapse-free rates).

The rates of grade 3 or 4 toxicity on the two treatment arms will be compared using chisquare tests. Overall level of disability will be analysed using longitudinal statistical methods similar to those used for TESS. Statistical analysis for disease-free survival and overall survival will be based on one-sided 95% confidence intervals for the hazard ratio to assess non-inferiority.

Interim analysis

Interim analyses will be carried out annually and presented to an independent Data Monitoring Committee (DMC). The interim analyses will present recruitment data and data on all primary and secondary outcomes.

Final analysis

The study is expected to complete recruitment within 4 years. Final analysis will be carried out after all patients have been followed up for a minimum of two years.

Calculation of sample size

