Sample size calculations are based on the two primary outcome measures of limb function and time to local recurrence. In relation to limb function, a difference in TESS score between the two treatment arms of 10 points would indicate a clinical benefit to patients (Davis, personal communication). Previous data has suggested an expected standard deviation for the score of 20. The key analysis for this outcome measure is the difference in score at two years. Assuming a null hypothesis of no difference will be tested using a t-test with 5% significance level and assuming a standard deviation of 20, 105 patients per treatment arm will be needed to detect this size of difference at two years with 95% power.

In relation to local relapse, sample size is calculated based on showing that the 2-year local relapse rate on the experimental treatment arm is non-inferior to that on the control arm. The two-year local relapse-free rate on the control treatment is expected to be 80% and a decrease in this rate to 70% would be the largest difference between treatments that can be judged as clinically acceptable. A non-inferiority margin of 70% is therefore chosen as relevant for this trial. With 198 patients per arm with full follow-up for two years and using a one-sided 95% confidence interval there will be 80% power to detect non-inferiority in two-year local relapse-free rates of 10% or less.

In conclusion, with 200 patients per treatment arm, there will be 95% power to detect a difference of 10 points in the TESS score between the treatment arms at two years and 80% power to determine non-inferiority in local relapse-free rates with non-inferiority defined as a difference in two-year local relapse-free rates of 10%.

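### The early-stopping rule lets a limb-function difference alone end the trial, although the primary claim also needs non-inferior local control

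*Protocol*

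**What the plan says.** Section 6 (Analysis of outcome measures) states one joint primary hypothesis, that reduced volume "will improve limb function without compromising local control". Section 2 gives the same joint objective. For TESS, the sample-size paragraph assumes a null hypothesis of no difference "tested using a t-test with 5% significance level", with 105 patients per arm for 95% power. For local relapse it asks for 198 per arm with full two-year follow-up, for 80% power.

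Interim analyses are annual, and "The interim analyses will present recruitment data and data on all primary and secondary outcomes". On timing, section 9 adds: "The committee will meet one year after the trial opens and then annually thereafter until the trial closes to recruitment".

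Section 9 then gives the stopping rule. It begins "The trial would also stop early if the interim analyses showed differences between treatments in terms of local relapse", limited to differences that clinicians would find unacceptable, and continues "or showed differences in limb functioning that was deemed to be convincing to the clinical community". The preceding sentence, on recruitment rate, data quality and patient safety, says only that the committee may consider stopping. This sentence says what would happen.

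**The concern.** The two stopping conditions are alternatives. Read as written, a persuasive functional difference ends the trial whatever is known about local relapse. The rule does not require non-inferiority to have been shown or still to be obtainable.

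Reduced volume is worth adopting only if local control holds, so a stop on function alone would deliver half of the claim and weaken the evidence for the other half. This is a realistic path, because function needs only about half the patients that relapse needs and is therefore likely to look settled first.

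A second consequence concerns the TESS test. The sample size spends the whole 5% at the final analysis, so any interim success route on TESS adds to the error rate by an amount the protocol does not fix.

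**Working it through.** **Inputs from the protocol.** TESS difference 10, SD 20, 5% level (taken as two-sided), 95% power. Two-year local relapse-free rate 80% on control, margin 10 percentage points, one-sided 5%, 80% power. Hazard-ratio margin 0.63. Recruitment 100 a year for 4 years. Final analysis after at least two years of follow-up for all.

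**Assumptions.** Uniform accrual, no dropout, 1:1 allocation, true relapse-free rate 80% in both arms. For event counts, also a constant hazard and no deaths.

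**1. The plan's own sample sizes.**
- TESS: n = 2(1.96 + 1.645)² × 20²/10² = 104 per arm by the normal approximation. The exact t calculation gives 95.0% power at 105. This reproduces at the full 5%, with nothing reserved for interim looks.
- Local relapse: n = (1.645 + 0.842)² × 2 × 0.8 × 0.2/0.10² = 198 per arm. This reproduces.
- Hazard-ratio margin: ln 0.8/ln 0.7 = 0.626, stated as 0.63.

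**2. When two-year TESS is available.** None at the year-1 and year-2 looks, about 100 patients (50 per arm) at year 3, and about 200 (100 per arm) at year 4.

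**3. Chance that function looks persuasive early**, if the true difference is 10 points (two-sample t-test, standardised difference 0.5):

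| Look | p<0.05 | p<0.001 |
|---|---|---|
| Year 3, 50 per arm | 70% | 20% |
| Year 4, 100 per arm | 94% | 58% |

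**4. Non-inferiority power after a stop.**

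(a) Recruitment stops, but everyone recruited is followed for two years. Power = Φ(0.10/√(2 × 0.8 × 0.2/n) − 1.645), with n per arm:
- Year 2, n = 100: Φ(1.768 − 1.645) = 55%.
- Year 3, n = 150: Φ(2.165 − 1.645) = 70%.
- Year 4, n = 200: Φ(2.500 − 1.645) = 80%, so nothing is lost.

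(b) Analysis at the moment of a year-3 stop. The hazard is −ln(0.8)/2 = 0.1116 a year. Expected relapses = 100 × [3 − (1 − e^(−0.1116 × 3))/0.1116] = 45. Power = Φ(0.469 × √45/2 − 1.645) = 47%, where 0.469 = −ln 0.626. (With the rounded 0.63 it is 46%.) In this model the full trial yields about 142 relapses and about 87% power. A year-3 stop followed by two more years yields about 96 relapses and about 74%, close to the 70% in (a).

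**5. TESS type I error**, with looks at years 3 and 4 and a final test at 5%. Information fractions are 100/400, 200/400 and 1. Results are from simulating correlated Z statistics (4 million runs):

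| Interim threshold | Overall error |
|---|---|
| p<0.001 | 5.1% |
| p<0.01 | 6.1% |
| p<0.05 | 11.3% |

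**The case against.** Several points on the other side are sound.

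- **The looks are not shown to be unadjusted.** A reader might infer that TESS is tested at p<0.05 each year and that the error rate more than doubles. The protocol names no interim threshold. A strict one leaves the error near 5.1%, and numeric boundaries are commonly set in an analysis plan or committee charter. For the same reason, the lack of a numeric relapse boundary is not a fault here. Nor does a 14% figure for five equally spaced looks fit this trial: meetings end when recruitment closes, which leaves two looks with two-year TESS, plus the final.
- **A stop need not leave local control unanswered.** A reader might infer that it would. But the committee's question is about continuing recruitment, the visit schedule runs to five years and beyond, and the final analysis waits for two years of follow-up. If follow-up continues, a year-3 stop keeps about 70% power and a year-4 stop costs nothing. The protocol does not settle whether follow-up would continue.
- **The committee sees relapse data at every look** and would use judgement.
- **Removing the limb-function clause altogether would go too far.** It has no direction, so it also covers worse function on the research arm.

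These points limit the size of the problem but do not remove it. A numeric TESS boundary in another document would control the error rate and still leave a stop on one half of a joint hypothesis. Judgement is a weak safeguard when the text says that function alone would suffice.

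**Conclusion.** The point holds as a conflict within the protocol: section 9 allows a stop on function alone, whereas sections 2 and 6 make the claim joint and section 6 sizes the trial for local relapse.

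The loss depends on timing and on follow-up. A year-3 stop leaves about 70% non-inferiority power with two-year follow-up of the 300 recruited, or about 47% if analysed at the stop, against the planned 80% (about 87% in the event-based model used for the 47%). A year-4 stop costs power only if follow-up also ends. A year-2 stop would leave about 55% with full follow-up, but it would have to rest on TESS scores taken before two years.

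The effect on the TESS error rate is conditional. It runs from about 5.1% to 11.3% according to the threshold applied, and the documents do not support any single value. These figures rest on uniform accrual, no dropout and equal true relapse rates in the two arms.

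**What to change.** Revise the interim-analysis text in section 6 and the Data Monitoring Committee paragraph in section 9 to state that:

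1. A limb-function benefit on the research arm does not by itself stop recruitment, end relapse follow-up or replace the planned non-inferiority analysis.
2. Early stopping on outcome data is for harm: excess local relapse, safety, or worse function on the research arm.
3. TESS superiority is tested once, at the final analysis, at 5%.

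The numeric guideline for relapse can be left to the committee's charter. The cost is about one paragraph of text, and the sample size is unchanged. The sponsor gives up an early stop for function, which could not have supported the joint claim.
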